Appendix 2. SAS PROGRAMMING DETAILS

Appendix 2.1. Programming Confidence Bands for KM Survival Curve

- Use of PROC LIFETEST;
- Create an OUTPUT dataset containing the survival estimates;
- Use CONFBAND = HW to produce confidence bands for the method of Hall and Wellner in the PROC LIFETEST statement.

Appendix 2.2. Programming Confidence Intervals for KM Median Time to Event

- Use of PROC LIFETEST;
- Use CONFTYPE=LINEAR to produce confidence intervals for the method of Brookmeyer and Crowley in the PROC LIFETEST statement;

Sample SAS code:

```
proc lifetest data=mydata outsurv=estimates confband=HW conftype=linear  
timelist=182;  
    time Days*Status(0);  
run;
```

CCI [REDACTED]

[REDACTED]

[REDACTED]

[REDACTED]

[REDACTED]

[REDACTED]

[REDACTED]

[REDACTED]

[REDACTED]

[REDACTED]

[REDACTED]

[REDACTED]

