9.3.1. Analysis of Primary Endpoint

The primary efficacy variable will be time-to-event, where event is defined as the earliest occurrence any of the following:

- Loco-regional/distant recurrence of the primary breast cancer;
- Appearance of a second primary or contralateral breast cancer;
- Death due to any cause.

Time-to-event will be calculated as the time from date of enrollment to first objective documentation of the event defined above. In the analysis of time to event, subjects lost to follow-up and subjects who are still being followed at the time of analysis with no documented event will be censored at the last date the subject was known to be event-free.

The Kaplan Meier non-parametric estimate will be used to summarize the survival distribution and median for time-to-event. Ninety-five percent confidence intervals for the survival distribution will be computed.

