4. HYPOTHESES AND DECISION RULES

4.1. Statistical Hypotheses

This study is non-comparative and no inferential statistical analyses are planned. Analyses will consist of descriptive statistics and corresponding 95% 2-sided confidence intervals when appropriate.

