8.1.2. Analyses for Categorical Data

For dichotomous variables (proportions, incidences and HER2 status), the number and percent of subjects will be presented. A two-sided 95% confidence interval (Wilson score interval) will be presented for the percent.

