8.2. Statistical Analyses

8.2.1. Efficacy Analyses

All summaries of efficacy parameters will be reported within the FAS population. Analyses will be primarily descriptive in nature, and therefore no statistical sample size estimation was performed.

Primary analysis

The primary analysis is time-to-recurrence, where recurrence is defined as the earliest occurrence any of the following:

- Locoregional/distant recurrence of the primary breast cancer.
- Appearance of 2nd primary or contralateral breast cancer.
- Death due to any cause.

Time-to-recurrence is calculated as the time from date of enrollment to first objective documentation of the recurrence defined above. In the analysis of time to recurrence, subjects lost to follow-up and subjects who are still being followed at the time of analysis with no documented event will be censored at the last date the subject was known to be event-free. The Kaplan Meier non-parametric estimate will be used to summarize the survival distribution and median for time-to-event. 95% confidence interval for median time to event (method of Brookmeyer and Crowley 1982) and 95% confidence bands for the survival distribution (method of Hall and Wellner, 1980) will be computed.

Secondary analyses

Locoregional/distant recurrence, appearance of 2nd primary or contralateral breast cancer, and death will also be summarized as follows:

- Time to each event will be summarized similarly as the primary analyses for time-to-recurrence (See [Section 8.1.3](#)).
- Summary statistics for the proportion of subjects experiencing each event.
- Summary statistics for the incidence rate (per annum), defined as a ratio of the number of events and the total exposure time (in years) to Aromasin[®] therapy.

CCI [REDACTED]

[REDACTED]

[REDACTED]

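### The sample Kaplan-Meier code puts pointwise survival limits on the linear scale, which under-covers on the optimistic side when few events have occurred

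*SAP*

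**What the plan says.** Protocol 9.3.1 commits, for the primary endpoint, to the following: "Ninety-five percent confidence intervals for the survival distribution will be computed". SAP 8.2.1 words the curve limit differently: "95% confidence bands for the survival distribution (method of Hall and Wellner, 1980) will be computed". SAP 4.1 sets the level for the whole plan: "corresponding 95% 2-sided confidence intervals when appropriate".

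The programming detail is in SAP Appendix 2. Appendix 2.1 covers the band and names no transform: "Use CONFBAND = HW to produce confidence bands for the method of Hall and Wellner in the PROC LIFETEST statement". Appendix 2.2 is headed for the median and says: "Use CONFTYPE=LINEAR to produce confidence intervals for the method of Brookmeyer and Crowley in the PROC LIFETEST statement". Its sample code puts both requests, and the output data set of survival estimates, into one statement: "proc lifetest data=mydata outsurv=estimates confband=HW conftype=linear". The same statement continues with TIMELIST=182.

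SAP 8.2.1 carries the approach to the component events: "Time to each event will be summarized similarly as the primary analyses for time-to-recurrence". For simple proportions, SAP 8.1.2 takes a different line: "A two-sided 95% confidence interval (Wilson score interval) will be presented for the percent".

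**The concern.** The linear option is there for the median, which SAP 8.1.3 reports only if it can be estimated and which is unlikely to be reached in 2-3 years of observation. Run as written, the call also builds each pointwise survival limit as the estimate plus or minus 1.96 Greenwood standard errors. That is the Kaplan-Meier counterpart of the Wald interval for a proportion. It behaves badly when the estimate is close to 1 and rests on few events. Day 182, the only time point in the code, is where that is most likely.

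This is a single-arm study without hypothesis tests, so intervals carry the whole statement of precision. Limits that are too short, and miss mainly by lying above the true event-free probability, flatter the treatment. The plan also treats like quantities unequally: an event reported as a simple proportion gets a Wilson interval, while the same event reported as a Kaplan-Meier estimate gets a Wald-type one.

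**Working it through.** **Inputs from the documents.** Two-sided 95% level, so z = 1.96 (SAP 4.1). About 550 patients (Protocol 9.2). Treatment for 2-3 years, with observation ending when therapy ends (Protocol 3 and 9.2). Day 182 (SAP Appendix 2.2).

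**Assumptions.** Neither document gives an event rate, an expected number of events or a sample size calculation (Protocol 9.1). Event probabilities and censoring are therefore assumed. The only stated figure to test is the nominal 95%.

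**Formulas.** Let S be the estimate and SE its Greenwood standard error; without censoring, SE = √[S(1−S)/n].
- Linear: S ± 1.96·SE.
- Log-log: S^exp(±θ), with θ = 1.96·SE / (S·|ln S|).

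**One sample.** Take 6 events in 550. S = 544/550 = 0.9891 and SE = √(0.9891 × 0.0109/550) = 0.00443.
- Linear: 0.9891 ± 0.0087, giving 0.980 to 0.998.
- Log-log: θ = 0.0087/(0.9891 × 0.01097) = 0.80, giving 0.976 to 0.995.

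If the true event-free probability is 0.98 (11 events expected), the linear lower limit, 0.9804 before rounding, already lies above the truth. The same holds for every count from 0 to 6, and the binomial probability of 6 or fewer is 7.7%.

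**Exact binomial coverage, n = 550, no censoring before the time point.**

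| True event probability | Linear coverage | Interval wholly above truth | Interval wholly below truth | Log-log coverage |
|---|---|---|---|---|
| 1.0% | 90.8% | 8.7% | 0.4% | 97.1% |
| 1.5% | 90.5% | 8.5% | 1.0% | 94.8% |
| 2.0% | 91.5% | 7.7% | 0.9% | 95.5% |
| 3.0% | 93.1% | 5.9% | 1.0% | 95.6% |

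At 1.0% the log-log column counts zero-event samples (0.99^550 = 0.4%) as misses.

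The shortfall shrinks as events accumulate. Linear coverage is 94.0% at an event probability of 4%, 93.4% at 5%, 94.6% at 6%, 94.1% at 8% and 95.0% at 10%. It moves up and down because counts are discrete, so averages are the safer summary:
- S of 0.90-0.95: 94.5%, with 72% of misses optimistic.
- S of 0.95-0.98: 93.8%, 81% optimistic.
- S of 0.98-0.99: 92.3%, 91% optimistic.

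The log-log averages over the same ranges are 95.1%, 95.4% and 96.1%, the last without counting undefined zero-event samples as misses.

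**With censoring (simulation).** Assume a hazard of 3% per year, observation ending uniformly at 24-36 months and 5% per year drop-out. At day 182 the true S is exp(−0.03 × 182/365.25) = 0.985. Linear coverage there is 89.5% and log-log 95.3%. Linear coverage is 94.4% at month 12 and 94.7% at month 24. For a rarer event (3-year S = 0.97, 3% per year loss), linear coverage is 91.0% at one year and 93.9% at two.

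**No events yet.** Then S = 1 and SE = 0, so the linear interval has zero width, and the log-log interval is undefined.

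**Median.** Under a constant hazard, a median within 3 years needs ln 2/3 = 0.231, about 23% per year.

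**Hall-Wellner band.** Simulated simultaneous coverage at n = 550 on the linear scale is 96.4-99.7% for 3-year S from 0.85 to 0.99. Moving the band to log-log changes coverage from 97.1% to 96.1% (3-year S = 0.90), from 96.6% to 93.9% (0.97) and from 99.7% to 89.8% (0.99). The median lower band limit at day 182 falls from 0.949 to 0.881 when 3-year S is 0.90.

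**The case against.** The strongest reply is that the SAP text never names pointwise limits. For the curve it names the Hall-Wellner band, and the written instruction on the linear scale concerns the median alone, where linear is the usual form of the cited method. The combined call is labelled as sample code. On that reading, the protocol's intervals are supplied by the band, which does not under-cover. This stands as far as it goes. It does not dispose of the point, because the protocol says intervals, the code asks for output at a single day, and nothing visible gives another scale for those limits.

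A reader might infer several stronger things that the documents and figures do not support:
- That every Kaplan-Meier limit is too short. The band is conservative on the linear scale.
- That the problem runs across event-free proportions of 0.90-0.99. At n = 550 it is small below about 0.95 and absent at 0.90. That range is itself an assumption.
- That misses are almost always optimistic. This fits S of about 0.98 and above. At 0.90 the split is 3.4% to 1.6%, about two thirds.
- That HER2 subgroup curves are affected. The visible HER2 method is a Cox hazard ratio (SAP 8.1.3), the sample call has no STRATA statement, and the documents give no subgroup size. Some nearby text is redacted, so neither reading can be confirmed.

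**Conclusion.** The point holds in a narrow form. If the sample code is run as written and its pointwise limits are reported, those resting on few events fall short of 95% by about 2 to 4.5 points at n = 550 for true event probabilities of 1-3%. Optimistic misses are then two to three and a half times the nominal 2.5%. The composite at day 182 and rare component events are the cases that matter; later composite estimates are close to nominal.

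The sizes depend on assumed event rates and censoring. The mechanism does not: a symmetric interval around an estimate near 1 is too short on the lower side whenever events are few. SAP 4.2 has no decision rules, so no conclusion of the study turns on this. It is a low-cost improvement to reported precision.

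**What to change.** In SAP Appendix 2.2, add a separate PROC LIFETEST call with CONFTYPE=LOGLOG that produces pointwise survival limits at named times, for the composite and for each component event. Keep CONFTYPE=LINEAR in the existing call for the median interval and the Hall-Wellner band. Changing the option in the existing call would move the band as well and could introduce under-coverage that is not there now.

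Where no event has occurred by a named time, state an exact one-sided lower bound and its level. For example, with 550 patients still at risk, a 97.5% bound is 0.025^(1/550) = 0.993.

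Add a sentence to SAP 8.1.3 saying that pointwise intervals at those times are reported alongside the band, so that Protocol 9.3.1 (intervals) and SAP 8.2.1 (bands) agree.

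The cost is one extra call, a few lines of text and slightly less favourable lower limits (0.976 instead of 0.980 in the six-event example).
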